Although the efficacy of LCPT has been shown for use in kidney transplant patients, there is still a need for observing medication adherence with regards to the once a day treatment. This study will look at medical adherence with regards to its outcomes in kidney transplant recipients in order to better understand how a once a day regimen of tacrolimus may be beneficial to patients. Drugs work in a dose and time dependent manner and more emphasis is being put on electronic monitoring of medication adherence (Vrijens & Heidbuchel, 2015). This study may utilize Medisafe Medication Manager to accurately track adherence of the study medication.

C Study Objectives

C1 Primary Aim

Aim 1: To determine whether an immunosuppressive maintenance regimen of Envarsus/azathioprine regimen compared to a tacrolimus/ mycophenolic acid regimen is associated with better compliance and tolerability. This may be examined by a survey to the patients at 3 and 12 months. In addition, for patients with smart phone, we may examine their adherence through “Pill Manager by Medisafe” app. This app tracks missed/taken doses.

C2 Secondary Aim

Aim 2: To determine whether an Envarsus/azathioprine regimen compared to a tacrolimus/ mycophenolic acid regimen is associated with a lower composite endpoint of biopsy proven acute rejection, graft loss, death and lost to follow up at 12 months after kidney transplantation. Biopsy will be performed if clinically indicated

C3 Rationale for the Selection of Outcome Measures

Acute Rejection:

We do not perform a protocol biopsy in our center, however, we have a low threshold to do a biopsy if there is an increased creatinine, proteinuria (urine protein/ creatinine > 1 gram), or de novo DSA with high level MFI. The decision of the biopsy will be based on

the decision of the clinician. Acute rejection can lead to failure and loss of the grafted kidney and is an important endpoint in many kidney transplant studies.

Graft Failure:

Graft failure will be defined by the return to hemodialysis, re-transplantation, or patient death. Death-censored graft failure will be defined as the return to hemodialysis or re-transplantation. Graft failure was chosen due to its importance in patient outcome.

Adherence:

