We will approach patients after transplantation. Patients will either receive tacrolimus or Envarsus based on insurance coverage. We will approach patients for the study after we have determined the form of calcineurin inhibitor they will be taking. If the patient consents to the study, we will enroll patients until we reach 50 patients in each arm of the study. If needed, the antimetabolite may be transitioned to the once or twice daily dosed medication, prior to discharge so that they may receive the medications prior to their discharge from the hospital. Because this is an open label study, blinding is not conducted.

3.d Preparation and Administration of Study Drug

Study medications may be self-administered by the patient. When not on the study site, all medications will be ordered through patient's preferred pharmacy. Suggestion will be made to utilize only subspecialty pharmacies.

3.e Subject Compliance Monitoring

We may use "Pill Reminder by Medisafe" for recipients who have I-phone or android smart device. Installing the app will take place before discharge. Records from the smart phone will be emailed from the device at the clinic visit at months 3 and 12. We understand that not all patients may have a smart device/phone, and so we plan to also use a survey – BAASIS. The BAASIS survey may be distributed at months 3 and 12. Average variability in tacrolimus levels for the follow-up period preceding each of the surveys may be calculated and compared between the two groups. Pharmacies may be contacted to assess for timing between refills to ensure that patients have taken medication as scheduled.

3.f Prior and Concomitant Therapy

Patients will receive induction therapy with either anti-thymocyte globulin or basiliximab at the time of transplantation. Depending on patient's prior medical history, they may have had prior immunosuppression and may be on immunosuppression prior to their transplant. This will not interfere with the study protocol or eligibility except if they meet exclusion criteria.

3.g Packaging

Study drugs will be packaged according to standard procedures for the medication.

3.h Blinding of Study Drug

This is an open label pilot study. The patients and study members will not be blinded to the study drug.

3.i Receiving, Storage, Dispensing and Return

Study medications may be self-administered by the patient. Study medications may be administered at the study site or ordered through patient's preferred pharmacy.

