At each study visit, we will collect the data as described in the study table and in the protocol description. The PI or study staff will review the data on an ongoing basis and every quarter for accuracy and completeness. Adverse effects will be routinely reviewed and recorded at each visit. Additionally any adverse event reported to the transplant physician, transplant coordinator or study coordinator including emergency department evaluation and/or hospitalization will be reviewed and documented by the principal investigator. Adverse event reporting will be done per the study agreement.

The study team will meet quarterly to review outcomes and safety of patients enrolled in the study as well as AEs. SAEs will be reviewed per occurrence.

10.f Reporting Procedures

Adverse events will be recorded at each medical visit. With the occurrence of an AE, an Adverse Event Log will be filed for the patient and put up for review by the PI.

In the instance of a SAE, an Serious Adverse Event Log will be filed and shown to the PI with every occurrence.

10.g Adverse Event Reporting Period

AEs will be reported to the IRB at the time of continuing review. SAEs will be reported according to IRB policy.

F11 Study Outcome Measurements and Ascertainment

- Acute Rejection:

We do not perform a protocol biopsy in our center, however, we have a low threshold to do a biopsy if there is an increased creatinine, proteinuria (urine protein/ creatinine > 1 gram), or de novo DSA with high level MFI. The decision of the biopsy will be based on the decision of the clinician.

- Graft Failure: Graft failure will be defined by the return to hemodialysis, re-transplantation, or patient death. Death-censored graft failure will be defined as the return to hemodialysis or re-transplantation.

- Adherence:

App: We will use “Pill Manager by Medisafe” for recipients who have I-phone or android smart device. Installing the app will take place before discharge. Records from the smart phone will be emailed from the device at the clinic visit at months 3 and 12.

Survey: Survey will be distributed at months 3 and 12. Other surveys will be also distributed to examine any possible side effects.

Tacrolimus level variability: Average variability in tacrolimus levels for the follow-up period preceding each of the surveys will also be calculated and compared between the two groups

Antimetabolite refill records:

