Pharmacies will be contacted to assess for timing between refills to ensure that patients have taken medication as scheduled.

Additionally, CBC, BMP or Renal panel (including creatinine, eGFR) Tac trough levels will be checked once a week for the first four months then once every other weeks as part of standard of care labs post transplant. These will be collected as data points during the study duration.

G Statistical Plan

G1 Sample Size Determination and Power

This is a pilot study. The number of patients was chosen to see if any initial evidence can be found for further investigation.

G2 Analysis Plan & Statistical Methods

Recipient characteristics will be described using proportions for categorical variables, and means with standard deviations for continuous variables. Recipient and donor factors will be compared among the groups (one a day medication group vs twice a day medication group) using a χ^2 or Fisher test for categorical variables and analysis of variance test or Kruskal Wallis tests for continuous variables, depending on the distribution of the variable.

Allograft and recipient survival will be assessed using the Kaplan-Meier survival analysis, and P values will be calculated using the log-rank test. Multivariate analysis using the Cox model will be used to calculate the hazard ratio during the follow up period for allograft failure and recipient death.

Adherence will be divided according to the level of adherence (score) into tertiles. Logistic regression will be used to examine the association between adherence and the medications group.

H Data Handling and Record Keeping

H1 Confidentiality and Security

Subject privacy: During the study we will perform medical history and examination at each recurring visit as part of standard follow-up and usual care post-transplant. Labs will be done per standard of care, and collected at each time point until 12 months post-transplant. All information collected will be for research purposes only and data will be kept in strict confidence. No information will be given to another party without the consent of the subject. We will be assigning patients a unique study number for de-identification purposes.

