Database protection: We will be keeping a database that will be secured with password protection. The person performing statistics will be receiving only de-identified information from the database. For paper documents such as source documents and questionnaires, these will be kept in separate participant charts that will be secured in a locked cabinet in the locked study coordinator office with access only for study personnel.

H2 Training

All lab personnel will be qualified to do their assigned work. All personnel working with PHI will have documented HIPAA training. Each team member will be noted on the Department Signature Sheet.

H3 Case Report Forms and Source Documents

CRFs will be created and kept in each person's file, tracking medications, FK levels, labs, and information regarding medication refills (See all attachments). All source documents including labs near the time of each scheduled visit that patients get outpatient, surveys, medication adherence pill monitoring system information, outpatient notes will be placed into each person's file.

H4 Records Retention

All research records, including signed consent forms, will be kept in their original form or a certified scanned electronic form for at least seven years beyond close of the study.

I Study Monitoring, Auditing, and Inspecting

I1 Study Monitoring Plan

The PI and study members will review the data on an ongoing basis and every quarter for accuracy and completeness.

J Study Administration

J1 Organization and Participating Centers

This study will be performed at Washington University School of Medicine.

J2 Funding Source and Conflicts of Interest

This study is funded by Veloxis Pharmaceuticals. Each study team member will declare any conflicts of interest to the IRB.

J3 Subject Stipends or Payments

Participants will not receive any payment for the study nor study medication, which patients will receive through their insurance coverage.

J4 Study Timetable – Table 1

Study event	Visit number						
	Visit 0 – post surgery	Visit 1- 2-4 weeks	Visit 2 – 5-8 weeks	Visit 3 – 9-12 weeks	Visit 4 – 6 months	Visit 5 – 9 months	Visit 6 – 12 months
Inclusion/Exclusion	X						
Informed consent	X						
Contact/demographics	X						
Medical history	X						
Physical exam	X						
Medisafe med manager taught	x						
Med dosages given/recoded	x						

Patient verbal consent to continue study		X	X	X	X	X	X
Reconsent if needed		X	X	X	X	X	X
Evaluate for AEs		X	X	X	X	X	X

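### Cutting the adherence score into sample tertiles before logistic regression gives up some power if scores are spread out, and makes the result depend on an unwritten tie rule if many patients share the best score

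*Combined protocol and SAP*

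**What the plan says.** Section G2 gives adherence two sentences. The first is "Adherence will be divided according to the level of adherence (score) into tertiles". The second is "Logistic regression will be used to examine the association between adherence and the medications group". G2 does not state the cut-points, how patients tied at a boundary are placed, or whether the model is binary, ordinal or multinomial. It gives no model for the uncut score.

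G2 also does not say which score or visit is meant. C1 says of the app, "This app tracks missed/taken doses". F11 says "Survey will be distributed at months 3 and 12", while E3 3.e is softer: "The BAASIS survey may be distributed at months 3 and 12". F11 also plans a separate comparison of tacrolimus level variability, which "will also be calculated and compared between the two groups".

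G1 describes a pilot with no power calculation: "The number of patients was chosen to see if any initial evidence can be found for further investigation". H3 has the raw adherence material retained: "surveys, medication adherence pill monitoring system information, outpatient notes will be placed into each" participant's file.

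**The concern.** Tertiles of the sample replace the score with three ranks whose boundaries are set by whoever happens to be enrolled. The consequence depends on the shape of the score.

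- **Spread-out score** (for example, a dose count from the app): grouping discards information that has been collected. How much depends on the unstated model type.
- **Many patients at the best score:** equal thirds cannot be formed, and someone must decide where the tied patients go. That decision is unwritten and could be made after the data are seen, in an open-label study.

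In both cases the planned analysis reports no adherence proportion at a fixed cut-point. Sample tertiles do not carry over to another study, so they serve the purpose in G1 poorly. A fixed-cut proportion with an interval could be used to plan the next trial.

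**Working it through.** The plan states no power, effect size or significance level, so there is no figure of its own to reproduce.

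**Inputs.** From the documents: 50 per arm (E1), with 100 patients intended to complete (E2 2.b). Assumed: one visit; two-sided 0.05; a normal score with shifts of 0.4, 0.56 and 0.7 SD for the spread-out case; for the tied case, a five-level score, 40 to 65% at the best value, and an odds ratio of 2.5.

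**1. Information kept by tertiles.** For a normal score the cut-points lie at ±0.431 SD, where the density is φ = 0.3636.
- One tertile versus the rest: φ²/[p(1−p)] = 0.1322/0.2222 = 0.59.
- Ordered tertiles scored −1, 0, 1: (2φ)²/(2/3) = 0.5288/0.6667 = 0.79.

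So 100 patients carry the information of about 79, or about 59.

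**2. Power with a spread-out score.** The uncut (Wilcoxon) and ordered-tertile figures come from 10,000 simulated trials per shift. For one tertile versus the rest, power = Φ(5 × shift × √0.59 − 1.96), where 5 = √(50/2) and √0.59 = 0.771:
- 0.4 SD: Φ(−0.42) = 34%
- 0.56 SD: Φ(0.20) = 58%
- 0.7 SD: Φ(0.74) = 77%

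| Shift | Uncut | Ordered tertiles | Loss (points) | One tertile v rest | Loss (points) |
|---|---|---|---|---|---|
| 0.4 SD | 48.5% | 42.0% | 6.5 | 34% | about 15 |
| 0.56 SD | 76.9% | 69.6% | 7.3 | 58% | about 19 |
| 0.7 SD | 92.4% | 87.5% | 4.9 | 77% | about 15 |

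**3. When ties interfere.** With 100 patients, groups of 33/33/34 are possible with 34 tied at the best score but not with 35. If tied patients are kept together, three groups are impossible once 67 tie, because both cut-points then fall on the best score. Exact binomial probabilities:
- 35 or more tied: 87% at a true share of 40%, over 99.9% at 50%.
- 67 or more tied: 9% at 60%, 38% at 65%.

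**4. Power under each tie rule** (10,000 trials per case, odds ratio 2.5):

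| Share at best score | Uncut | Ties up | Ties down | Random split | Up and down disagree on p<0.05 |
|---|---|---|---|---|---|
| 40% | 70.8% | 67.7% | 62.2% | 64.5% | 19.6% |
| 50% | 67.6% | 66.4% | 60.5% | 57.2% | 15.5% |
| 60% | 63.2% | 62.1% | 55.1% | 50.3% | 13.0% |
| 65% | 59.7% | 58.1% | 36.7% | 45.2% | 24.6% |

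Losses against the uncut analysis are 1 to 3 points (up), 7 to 23 (down) and 6 to 15 (random). A separate simulation gave 12 to 20% disagreement, so the overall range is about 12 to 25%. With no true difference, type I error under these rules was about 3 to 6%.

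**5. The alternative.** In 1,500 trials per case at odds ratio 2.5, a proportional-odds likelihood-ratio test had power 64.5% against 63.8% for Wilcoxon at a 60% share, and 61.3% against 60.7% at 65%. Type I error was 5.3% and 5.9%.

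The 95% half-width for a risk difference is 1.96 × √{[p₁(1−p₁) + p₂(1−p₂)]/50}:
- 70% v 80%: 1.96 × √(0.37/50) = 0.169
- 60% v 70%: 1.96 × √(0.45/50) = 0.186
- 50% v 60%: 1.96 × √(0.49/50) = 0.194

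**The case against.** The strongest reply is that this is a pilot with no power target, so 5 to 7 points under an ordinal model alter no stated decision. That stands, and it limits how much weight the power loss can bear.

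It is also fair that ties are hypothetical. The BAASIS scoring is in an attachment not shown here, and a dose-level score from the app might rarely tie. Placing ties up is nearly harmless. The suggested replacement is not free of disagreement either: the uncut and fixed-cut analyses differ on p<0.05 in 8 to 16% of the same simulated trials. Naming one as the main analysis limits that harm.

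What does not stand is that this is merely missing detail. G2 commits to a method, and a better one exists for data already scheduled.

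A reader might infer stronger versions that the documents do not support:
- **A larger loss for a binary model.** At 0.4 SD, simulated power is 27% for a tertile of 33 but 36% for one of 34. Top and bottom tertiles have equal power under this shift. The gap arises because exact type I error is 3.3% for 33 and 5.7% for 34. The efficiency-based 15 to 19 points is the fair figure.
- **A tied share taken from B1.** Its estimate of non-adherence above 30% does not fix the share reaching the best value on this score.
- **False positives.** The three tie rules do not materially inflate type I error. Breaking ties by file order in a file sorted by arm would, but nothing in the documents suggests that.
- **No model-free comparison of adherence at all.** F11 does plan one, for tacrolimus variability.

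**Conclusion.** The concern holds in conditional form. Tertiles cost about 5 to 7 points of power if the score is spread out and the model is ordinal, and roughly 15 to 19 if one tertile is set against the rest. If 40 to 65% of patients share the best score, the result depends on an unwritten rule costing anywhere from 1 to 23 points, and two reasonable rules disagree on significance in about 12 to 25% of trials.

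The effect sizes, distributions, tied shares and significance level are all assumptions; the documents supply only the 50 per arm. Because the pilot has no power target, the open choice of model and tie rule matters more than the power loss. This is a cheap improvement worth making, not a flaw that invalidates the study.

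**What to change.** Replace the two adherence sentences in G2 with wording along these lines, filling the brackets before analysis:

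*The adherence score from [named source] at month [3 or 12] will be analysed uncut by proportional-odds logistic regression on medication group, with [any covariates named in advance]; the other visit is supporting. The proportion non-adherent, at a cut-point fixed before analysis, will be given by group with the risk difference and 95% CI.*

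A rank-based comparison would serve equally for an unadjusted analysis. If the survey yields only yes or no, the fixed-cut proportion with binary logistic regression becomes the main analysis.

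The cost is two sentences, and no new data if the survey is given as F11 and the study timetable (Table 1) schedule it. The downsides are the proportional-odds assumption and an odds ratio that is slightly harder to explain. With 50 per arm the risk difference is known only to about ±17 to 19 points. The change does not address confounding from the non-randomised, insurance-based assignment (E2 2.c, E3 3.c), so the wording should leave room for covariate adjustment.

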- Combined organ transplant
-
- Discharge to an acute-care facility after transplant

2.a Ethical Considerations

All patients will be given actual immunosuppressive medications (not placebo) in combinations that we have used in other patients at our transplant center. The only difference is one group will have medications dosed once a day and the other group will be on medications that are dosed twice a day, as per the medication administration recommendations.

2.b Subject Recruitment Plans and Consent Process

We will enroll 50 patients in each arm at the time of transplantation. Accounting for dropout of 20% from the study, we plan to possibly need to consent 120 patients total to obtain the 100 patient total number who complete the study. Subjects that meet the study inclusion criteria and without exclusion criteria will be approached in person prior to discharge from the hospital. The consenting process will be done in person by a study team member. Patients will be given the opportunity to look over the consent form and ask questions. A copy of the signed consent form will be provided to the patient once signed. Patients will be seen as part of the study until month 12 (+/- 29 days) from the time of transplant.

2.c Randomization Method and Blinding

We will approach patients after transplantation, prior to discharge. If patients are eligible to receive either tacrolimus or Envarsus, then we will approach them for participation in the study. If the patient consents to the study, we will enroll patients until we reach 50 patients in each arm of the study. There is no randomization done. Because this is an open label study, blinding is not conducted.

2.d Risks and Benefits

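### Arms follow insurance coverage, yet section G2 prespecifies no adjustment for the adherence comparison and attaches no consequence to its baseline comparisons

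*Combined protocol and SAP*

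**What the plan says.** **Allocation.** Section E2 2.c states: "There is no randomization done". Section E3 3.c gives the rule that replaces it: "Patients will either receive tacrolimus or Envarsus based on insurance coverage". The drug is known before consent is sought: "We will approach patients for the study after we have determined the form of calcineurin inhibitor they will be taking". The antimetabolite may then be switched to match. Section J3 adds that patients obtain the study drugs through their insurance.

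**Aim.** Compliance is part of Aim 1 (C1), which is worded as an association. The hypothesis in A2 is worded causally.

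**Analysis (G2).** Three sentences matter:
- Baseline: "Recipient and donor factors will be compared among the groups", by standard tests. No use of the result is stated.
- Graft failure and death: "Multivariate analysis using the Cox model will be used to calculate the hazard ratio". The covariates are not listed.
- Adherence, after a split of the score into tertiles: "Logistic regression will be used to examine the association between adherence and the medications group".

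Section F11 also plans a between-group comparison of tacrolimus level variability, again with no covariates named. Insurance class is not named as a variable to record or compare. The demographics form used at Visit 0 (F3) is not shown.

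**The concern.** Coverage decides the arm. It also governs how patients get their drugs during follow-up, and pharmacy refill timing is one of the planned adherence measures. Coverage can therefore plausibly affect adherence by routes other than dosing frequency. In a non-randomised comparison this is the first confounder to plan for. G2 foresees multivariate modelling for graft failure and death but not for the outcome in the primary aim.

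The study seeks a signal for later work, as section G1 says: "The number of patients was chosen to see if any initial evidence can be found for further investigation". A crude difference in adherence could send that work in the wrong direction, or hide a regimen effect, and the reader could not tell which. Because the study is open label and adherence is reviewed quarterly (F10 10.a), leaving the choice of covariates open also invites a choice made after the data have been seen.

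**Working it through.** The plan gives no figure to reproduce here: no significance level, power, effect size or expected imbalance. The point itself rests on the text. The arithmetic below only shows what size of bias is plausible.

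**Inputs from the documents.** 50 patients per arm (E1); adherence in tertiles (G2), so about 33 of 100 patients fall in any one tertile.

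**Assumed inputs.** No true regimen effect. One binary insurance class, with prevalence 0.5 + d/2 in one arm and 0.5 - d/2 in the other, where d runs from 0.2 to 0.5. Odds ratio between class and tertile of 1.5 to 3. Overall rate 1/3. Two-sided 5% tests.

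**1. Bias of the crude comparison.** The false difference is d x (rate in one class - rate in the other). The class rates are solved so that they average 1/3.
- d = 0.2, OR 1.5: 0.2 x (0.378 - 0.288) = 1.8 points
- d = 0.3, OR 2 (central case): 0.3 x (0.409 - 0.257) = 4.6 points, that is 35.6% against 31.1%, crude OR 1.23
- d = 0.5, OR 2: 7.6 points
- d = 0.5, OR 3: 0.5 x (0.451 - 0.215) = 11.8 points, crude OR 1.71

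The sign depends on which arm holds the favourable class, and this is unknown.

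**2. False rejection.** Exact enumeration of the Wald test on the log OR gives 4.6% with no confounding. In the four cases above, in order, it gives 5.0%, 7.2%, 12.0% and 23.0%.

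**3. Sampling error for scale.** 95% half-width = 1.96 x sqrt(2 x (1/3) x (2/3) / 50) = 18.5 points.

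**4. Do the baseline tests help?** Exact power for a binary factor at 50 per arm:

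| Imbalance | Chi-square | Fisher |
|---|---|---|
| 20 points | 54% | 46% |
| 30 points | 87% | 83% |
| 50 points | about 100% | about 100% |

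The tests often miss an imbalance only near 20 points, and only a recorded factor can be tested. At every size, nothing in G2 follows from a positive test.

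**5. What adjustment achieves.** With class itself in the model, the mean bias of the log OR in the central case falls from about 0.2 to about zero. The standard error rises about 5-10% at d = 0.2 to 0.3 (OR 2 to 3) and about 19-21% at d = 0.5. Mean squared error of the log OR (6,000 simulated studies per row, Monte Carlo error about 2%):

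| Scenario | Crude | Adjusted for class |
|---|---|---|
| d = 0.2, OR 1.5 | 0.199 | 0.209 |
| d = 0.3, OR 2 | 0.229 | 0.222 |
| d = 0.5, OR 1.5 | 0.231 | 0.271 |
| d = 0.5, OR 3 | 0.495 | 0.294 |

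If only a proxy is available that agrees with class in 70%, 80% or 90% of patients, the central 4.6 points falls to 3.9, 3.0 or 1.7.

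**6. Model size.** Arm plus one propensity score gives 33/2 = 16.5 events per term. Arm plus six separate factors gives 33/7 = 4.7. A simulated model of that size (an 80% proxy plus five factors unrelated to arm and outcome, which is unfavourable to the list) had a higher mean squared error than the crude model in the central case, 0.269 against 0.232.

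**The case against.** **This is a pilot with associational wording.** True, and it limits the harm. It explains the missing power calculation. It does not explain the lack of a plan for confounding when insurance sets the arm and A2 is worded causally.

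**G2 does not forbid covariates.** This stands. A reader might infer that the plan commits to an unadjusted analysis, but the text is silent. The defect is missing prespecification. Nor does the Cox model offer a worked contrast, because its covariates are unlisted too.

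**Adjustment may not pay.** This stands in part. Mean squared error is worse than crude in two of the four scenarios and only slightly better in the central one. The material therefore does not support replacing the crude result with a long covariate model. It supports one small adjusted model beside it.

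**The problem lies in the allocation, not in G2.** This stands in part. If coverage fully fixes the arm, insurance cannot be adjusted for and only its measured correlates can. The limitation statement then carries most of the weight.

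**Sections E2 2.c and E3 3.c.** A reader might infer a contradiction from "If patients are eligible to receive either tacrolimus or Envarsus, then we will approach them for participation in the study". It exists only if this means eligible for both drugs. If it means one or the other, the sentence agrees with E3 3.c. The wording needs clarifying, but no conflict is shown.

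**Conclusion.** The concern holds and should be fixed, at modest severity. Run as written, the adherence comparison in Aim 1 is confounded by insurance-related differences whose size and sign the documents do not give. Under the stated assumptions the bias is about 2 to 12 points, against a 95% half-width of 18.5 points. In the central case false rejection rises only from 4.6% to 7.2%, and the 23.0% figure needs both extreme inputs at once. A reader might infer that the trial's adherence result will be seriously wrong, or that adjustment would make it sound. The documents support neither. Every imbalance and odds ratio used here is assumed, as is the choice of one tertile as the event, since G2 does not say how the tertiles enter the logistic model.

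**What to change.** 1. Record insurance class at Visit 0 and tabulate it by arm.
2. In G2, prespecify one adjusted adherence model: medication group plus a single propensity score built from named baseline factors, not selected by baseline P values. Report it beside the crude result.
3. Include insurance class in the score if both arms contain patients of each class. Otherwise state that it cannot be adjusted for. This rule uses baseline data only, so it can be fixed in advance.
4. Apply the same adjustment to the tacrolimus variability comparison in F11.
5. State residual confounding as a limitation, and word conclusions, including those on A2, as associations.
6. Clarify whether E2 2.c means eligible for both drugs, so that it agrees with E3 3.c.

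**Cost.** A few sentences in G2, modest analysis work, and possibly one new field. Precision falls by the amounts in step 5 of the working. Those amounts are for one binary covariate, and a score estimated from several factors was not simulated. Where confounding is weak, total error may not fall, which is a reason to keep the crude result in view.
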